Date	11/13/2019
Title	Clinical Utility of Postoperative Hemoglobin Testing Following Vaginal Hysterectomy and Reconstruction for Symptomatic Pelvic Organ Prolapse
Principle Investigator	[name]
Sub-Investigators	[name]
Research Specialist	[name], MS
Department	Urogynecology
Hatton #	19-111

Introduction:

- Obtaining a complete blood count (CBC) on post-operative day (POD) 1 to assess postoperative hemoglobin levels is routine practice at our institution after pelvic reconstructive surgery.
- There is minimal data supporting this practice. Multiple studies throughout the gynecology literature suggest that this is not a necessary or cost effective strategy to assess for postoperative anemia. ^{2,6,9,11}
- Most patients who require blood transfusion or reoperation for bleeding will show clinical signs of anemia. ^{2, 6, 7, 11} It is necessary to consider the entire clinical picture before initiating blood transfusion for postoperative anemia. ¹
- Although the individual cost of each lab test is low, the cumulative cost of these tests is substantial. ^{2,9}
- The procedure of choice for prolapse repair by Cincinnati Urogynecology Associates, TriHealth Inc. is a vaginal hysterectomy (TVH) with concurrent apical, anterior, and posterior compartment native tissue repairs as indicated. A review of the literature failed to identify any studies that have looked specifically at the utility of postoperative CBC after vaginal hysterectomy with prolapse repairs.

Purpose of Study

- To determine if checking a routine CBC results in clinically relevant changes to patient care in women undergoing pelvic reconstructive surgery with vaginal hysterectomy for treatment of pelvic organ prolapse.

Hypothesis or Research Question:

- We hypothesize that there is minimal utility in the routine collection of POD1 CBC in patients undergoing TVH during vaginal prolapse repairs.
- We also hypothesize that the overall blood transfusion rate of our pelvic reconstructive patients is low, and that a more selective approach to CBC collection would be appropriate.

Background:

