Surgeons commonly check a CBC on patients after major gynecologic surgery. This is done to evaluate for postoperative anemia and to provide surgeon reassurance prior to discharging a patient home. There are more than 200,000 inpatient operative procedures completed for pelvic organ prolapse annually in the United States.⁵ Studies quote rates from, 87-99.6% of patients having a CBC drawn on POD1 and up to 1/3 of these patients requiring some intervention based on these results.^{6,7,11} Further evaluations of abnormal lab results may be additional blood work or more invasive procedures such as imaging tests or reoperation.

In recent years, multiple studies have shown that routine preoperative lab testing is not ubiquitously indicated for women undergoing gynecologic and urologic surgery. Thirty day outcomes do not change regardless of lab collection prior to surgery.³ The American Society of Anesthesia recommends against routine preoperative lab testing in the absence of clinical indications.¹⁴ Even with these recommendations, up to 40% of women receive un-indicated preoperative lab testing prior to urologic procedures.¹³ Similar to lab testing in the preoperative period, despite the high rate surgeons ordering postoperative labs, the clinical utility of a POD1 CBC has been called into question.

Throughout the gynecology literature, studies have identified multiple risk factors for a larger drop in hemoglobin on POD1 including hysterectomy at the time of pelvic surgery, midurethral sling placement at the time of prolapse repair, lower BMI, and the amount of IVF received in the OR.^{2,11} These findings were corroborated by additional studies, which also identified preoperative anemia, history of coagulopathy, and African American or Hispanic ethnicity as risk factors for postop blood transfusion.^{4,8,10,12} Although these patient and surgical characteristics have been identified as risk factors for postoperative anemia and transfusion, one study noted based on their data, that if they restricted CBC collection to patients with at 2 or more signs of anemia on POD1, 90% of their sample would not have required testing.⁷ Other studies have corroborated that almost all patients that ultimately require blood transfusion will show clinical signs of anemia.^{2,6,11}

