Similar retrospective studies included between 629-1105 patients in their chart review.^{2, 6, 7, 11} Based on the number of vaginal hysterectomies performed by our department annually, we anticipate five years of data collection will provide a comparable study size for this review. Our anticipated sample size will be approximately 800 patients.

Data Collection: Please see attached data collection sheet

- Charts of all patients having a total vaginal hysterectomy by one of our four fellowship trained urogynecologists during the study time frame will be identified and analyzed for inclusion and exclusion criteria.
- All charts meeting inclusion criteria will be included in the analysis.
- Each chart will be reviewed and the following variables collected for analysis:
 - Type(s) of prolapse repair(s)
 - Additional procedure for urinary incontinence at the same time as hysterectomy and prolapse repair – yes/no
 - Preoperative CBC collected within 30 days of surgery – yes/no
 - Preoperative hemoglobin
 - CBC collected the morning of POD1 – yes/no
 - POD1 hemoglobin
 - Change in hemoglobin from preoperative to postoperative collection
 - Change in hemoglobin level ≥ 2 – yes/no
 - Postoperative hemoglobin ≤ 10 – yes/no
 - More than one postoperative hemoglobin obtained – yes/no
 - Patient with objective signs of anemia (*persistent hemodynamic changes: pulse >100 beats per minute, blood pressure <90/60*) – yes/no
 - Patient with subjective signs of anemia (*dizziness, lightheadedness, weakness, pale, cool, diaphoretic*) – yes/no
 - Blood transfusion – yes/no
 - Estimated blood loss
 - IVF volume received intraoperatively
 - Length of surgery (in minutes)
 - Prophylactic heparin given preoperatively – yes/no
 - General demographic data including: name, DOB, age, race, BMI, medical comorbidities, parity, smoking history, menopausal status
 - Preoperative aspirin use – yes/no
 - Preoperative antiplatelet medication use (i.e.: Brilinta, Effient, Plavix) – yes/no
 - Stage of pelvic organ prolapse at preoperative appointment
 - Prior abdominal or pelvic surgery – yes/no
 - Patient readmitted within 30 days of surgery – yes/no

- Patient seen in emergency department within 30 days of surgery – yes/no
- Length of hospital stay (in days)
- Delay in discharge due to CBC results – yes/no

Intervention or experimental aspect of the study:

- No intervention will occur as part of this study.

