- There are no potential risks to the study population by any aspect of this study.

Statistical Analysis:

Demographic data will be described using frequency (percentage) for categorical variables and mean (standard deviation) or median (min, max) for continuous variables. The percentage of subjects with hemoglobin less than 10 g/dL at POD1 will be evaluated as well as the percentage of subjects with signs of anemia. Pearson product moment correlation coefficient will be employed to measure the association between postoperative hemoglobin level and perioperative variables such as age, BMI, blood loss, or length of surgery. The mean hemoglobin change from pre- to postoperative measurement in symptomatic subjects will be compared with that of asymptomatic subjects using Student's t-test. Multiple linear regression will be used to investigate risk factors impacting mean decrease in hemoglobin. On the other hand, multiple logistic regression will be used to investigate factors associated with the presence of signs of anemia.

Ethical Considerations:**Informed Consent:**

- Informed consent will not be required given the retrospective chart review design of this study.

Privacy Information:

- Extensive effort will be made to ensure and maintain participant confidentiality. All identifying information will be maintained in a secure area at all times. All communication between staff members regarding participant data will occur via the Subject ID number only. However, identifying information will be retained in the original/source documents.
- The Excel spreadsheet will be stored on a password protected, encrypted TriHealth computer for ten years following study closure, and then purged.

Cost/Budget:

- This study will incur no cost to the institution, the participants, or the investigators.

Estimated Period of Time to Complete Study	
When will study begin?	Winter 2019
Protocol Development Completed	2 weeks
Admin Review Time	2 weeks
IRB Approval	3 weeks
Data Collection	4 weeks
Data Analysis	2 weeks
Presentation Development (if applicable)	2 weeks
Manuscript Development (if applicable)	4 weeks
Journal Submission Process (if applicable)	4 weeks
Study Closure	2 weeks

When and how will results be disseminated?

- The results will be disseminated by way of an oral or poster presentation at a national meeting and with publication in a high-impact journal.

References:

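### Eight signs of anemia are recorded as two yes/no items and not tabulated against low hemoglobin, so the cited two-sign rule can only be bounded and no selective rule's performance is reported

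*Combined protocol and SAP*

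**What the plan says.** Data Collection introduces its list with "Each chart will be reviewed and the following variables collected for analysis". Two of the listed variables concern signs of anemia, each answered yes or no:

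- objective signs, described as "persistent hemodynamic changes: pulse >100 beats per minute, blood pressure <90/60";
- subjective signs, described as "dizziness, lightheadedness, weakness, pale, cool, diaphoretic".

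The list has no field for an individual sign and no count. The section also says "Please see attached data collection sheet"; that sheet is not in the text available for review.

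The Background reports one study's finding that, had its authors "restricted CBC collection to patients with at 2 or more signs of anemia on POD1, 90% of their sample would not have required testing". The second hypothesis is that "a more selective approach to CBC collection would be appropriate", with no rule named. The stated goal, at the end of the Background, concerns asymptomatic women.

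The Statistical Analysis section gives the percentage of women with POD1 hemoglobin below 10 g/dL "as well as the percentage of subjects with signs of anemia". It then compares mean hemoglobin change between symptomatic and asymptomatic women by t-test, and models the presence of signs by logistic regression. Signs are used throughout as present or absent.

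**The concern.** A claim that testing can be selective needs two quantities for each candidate rule: how many women would still be tested, and how many clinically relevant cases would fall among those not tested. The plan falls short in two separate ways.

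The first is in the data. Within an item, one sign and several signs look the same: a woman who is pale, cool and diaphoretic gets the same subjective entry as one who only felt dizzy. The one rule to which the protocol attaches both a threshold and a yield therefore cannot be evaluated exactly in this population.

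The second is in the analysis. Two marginal percentages do not show how many women with low hemoglobin had no signs. The section also does not say whether symptomatic means the objective item, the subjective item or either. At stake is whether the study can put figures on the selective approach it hypothesises. A later count analysis would mean reopening about 800 charts.

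**Working it through.** The sample size of approximately 800 is a feasibility figure, set from annual volume and similar studies. There is no formula to reproduce, so the check concerns what the recorded items can identify.

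**Inputs from the documents.** Objective signs 2; subjective signs 6; total 2 + 6 = 8; anticipated sample 800; cited share not needing testing under the two-sign rule 90%, so 10% still tested, or 0.10 × 800 = 80 women.

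**Step 1: which sign patterns can be classified.** Eight present/absent signs give 2^8 = 256 patterns. The objective item is positive in 2^2 − 1 = 3 objective patterns, and the subjective item in 2^6 − 1 = 63 subjective patterns.

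| Objective | Subjective | Patterns | One sign | Two or more | Rule status known? |
|---|---|---|---|---|---|
| no | no | 1 | 0 | 0 | yes (no signs) |
| yes | yes | 3 × 63 = 189 | 0 | 189 | yes (two or more) |
| no | yes | 63 | 6 | 57 | no |
| yes | no | 3 | 2 | 1 | no |

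So 190 patterns are classifiable and 66 are not. These are counts of patterns, not proportions of patients.

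**Step 2: bounds on the two-sign share.** It follows that

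P(both items yes) ≤ P(two or more signs) ≤ P(at least one item yes).

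The documents give no item frequencies, so the rates below are assumptions chosen to show a range.

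| Both | Objective only | Subjective only | Two-or-more share | Women of 800 | Share spared testing |
|---|---|---|---|---|---|
| 3% | 5% | 12% | 3% to 20% | 24 to 160 | 80% to 97% |
| 5% | 5% | 20% | 5% to 30% | 40 to 240 | 70% to 95% |
| 2% | 3% | 5% | 2% to 10% | 16 to 80 | 90% to 98% |

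In each row the cited figure (80 women, 90% spared) lies within the bounds or at their edge, so the data could neither confirm nor exclude it.

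**Step 3: a second illustration.** Assume each sign occurs independently in 4% of women.

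- At least one sign: 1 − 0.96^8 = 0.279, or 223 of 800.
- Exactly one: 8 × 0.04 × 0.96^7 = 0.240.
- Two or more: 0.279 − 0.240, which before rounding is 0.038, or 31 of 800.
- Both items positive: (1 − 0.96^2)(1 − 0.96^6) = 0.0784 × 0.217 = 0.017, or about 14 of 800.

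The two items would bound the group of 31 only between 14 and 223. Independence is not realistic, since dizziness and lightheadedness overlap; positive correlation would narrow the gap between 223 and 31.

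**Step 4: what the two items do allow.** An any-sign rule can be evaluated fully. If 50% to 90% of 800 women had no signs (assumed; n = 400 to 720) and none was transfused, the one-sided 95% upper limit on the transfusion rate among them is 1 − 0.05^(1/n): 0.75% at n = 400 and 0.42% at n = 720. The data for this calculation are on the variable list, but the Statistical Analysis section does not plan it.

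**The case against.** The strongest reply is that the study never undertook to test a count rule. The hypothesis names no count, and the goal contrasts women without signs to women with them, a split that the two items capture. The count rule is one cited finding. The next sentence of the Background and the Introduction appeal to the presence of clinical signs, without a number. All of this stands. A reader might infer that the study cannot support its selective-testing hypothesis, or that its rationale rests on the two-sign rule. The documents support neither: any-sign, objective-only and both-items rules remain testable, and the count rule is cited rather than adopted.

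Further points also stand:

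- The collapse is within items only. Tachycardia with hypotension and isolated dizziness fall in different items, and merge only if symptomatic pools the two.
- The attached data sheet may already hold separate fields.
- Reporting two percentages separately does not prevent a cross-tabulation, since both values sit in the same record, and the t-test does link signs to hemoglobin change. But a difference in means does not give tests saved or cases missed, so the analysis gap remains. It is distinct from the collapsing of signs.
- The documents do not say which signs the cited study counted, so recording these eight would not by itself make the 90% figure comparable.
- A count takes more abstraction effort than ticking a box at the first sign found, and it depends on how fully symptoms were charted.

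**Conclusion.** The point holds in a limited form. As listed, the two items support any-sign, objective-only and both-items rules but only bound a two-or-more-signs rule. Separately, no planned analysis reports the yield or the misses of any selective rule, although the second hypothesis is about selective collection.

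The classification result (66 of 256 patterns ambiguous) follows from the listed variables alone. The patient numbers (24 to 160 women in the first assumed set, 14 to 223 under independent 4% signs) rest on assumed frequencies and show only that the bounds can be wide. The data half of the point falls away if the attached sheet already records each sign; the analysis half does not. This is a worthwhile, inexpensive improvement to make before abstraction, not a flaw that invalidates the study.

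**What to change.** 1. Record each of the eight listed signs as its own yes/no field, or confirm that the attached sheet does. Derive the objective, subjective, any-sign and count variables from these fields, and state which of them defines symptomatic.
2. Add a table that sets each candidate rule (any sign, objective only, both items, two or more signs) against POD1 hemoglobin below 10 g/dL, transfusion and delayed discharge. Report the percentage still tested and the number of cases missed, with confidence intervals. The hemoglobin rows apply to women who had a POD1 CBC.
3. State beforehand how overlapping terms such as dizziness and lightheadedness are counted, and acknowledge that counts depend on charting. Present any comparison with the cited 90% as approximate.

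The cost is eight fields in place of two (a net six), drawn from notes and vital signs the abstractor already has to read, plus one table. Abstraction will take somewhat longer because every sign must be looked for in every chart, which matters for about 800 charts in a planned four weeks. The outcome variables are already on the list, so step 2 needs no new data apart from the sign count.

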Within our Division, the surgical procedure of choice to treat pelvic organ prolapse is a total vaginal hysterectomy with concurrent vaginal native tissue prolapse repairs. As standard practice, patients are kept overnight in the hospital for observation and a CBC is collected the morning on POD1. Studies in the gynecology literature have looked at the utility of routine CBC on patients after elective gynecologic surgery in general, total laparoscopic hysterectomy, minimally invasive sacrocolpopexy with or without concurrent hysterectomy, but none have looked specifically at our patient population having a vaginal hysterectomy with vaginal prolapse repairs.^{2,6,7,10}

Our goal is to show that routine collection of a CBC on POD1 in asymptomatic patients after vaginal hysterectomy with prolapse repair is unnecessary. If this is found, we could stop routine CBC collection which is a bothersome procedure for many patients and an added expense contributing to high health care costs.

Research Plan:

Study Design: Retrospective chart review

Setting of Study: TriHealth Epic platform at one of the various clinical locations.

Participants: All patients who underwent a total vaginal hysterectomy with concurrent vaginal native tissue prolapse repairs performed by one of four fellowship trained urogynecologists at TriHealth between 10/1/2014 and 10/1/2019. The patients will be identified by CPT codes in the EPIC electronic medical record.

Inclusion Criteria:

Total vaginal hysterectomy with or without bilateral salpingectomy/oophorectomy (CPT 58260, 58262, 58263, 58270, 58290, 58291, 58292, 58294)

At least one of the following vaginal native tissue prolapse repairs

Apical repair with uterosacral ligament suspension (CPT 57283)

Apical repair with sacrospinous ligament fixation (CPT 57282)

Anterior repair (CPT 57240, 57260, 57284, 57285, 57250)

Posterior repair (CPT 45560, 56800, 56810, 57200, 57210, 57250)

Age >18

Surgery by one of four fellowship trained urogynecologists at TriHealth

Exclusion Criteria:

Concomitant surgical procedure by a second surgeon

Malignancy identified at the time of surgery or active malignancy

Cases converted to open hysterectomy or prolapse repairs

Prolapse repair completed robotically

Prolapse repair completed with mesh

Known coagulopathy

Patient on long term preoperative anticoagulant medication (Arixtra, Coumadin, Eliquis, Heparin, Lovenox, Pradaxa, Savaysa, Xarelto)

Sample Size:

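### The study asks whether a routine POD1 CBC changes care, but no planned analysis takes a change in care as its outcome

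*Combined protocol and SAP*

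**What the plan says.** Purpose of Study sets the question: "To determine if checking a routine CBC results in clinically relevant changes to patient care". Hypothesis or Research Question adds "We also hypothesize that the overall blood transfusion rate of our pelvic reconstructive patients is low". The end of Background narrows the target, since the stated goal is to show that "routine collection of a CBC on POD1 in asymptomatic patients after vaginal hysterectomy with prolapse repair is unnecessary".

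Data Collection introduces its list with "Each chart will be reviewed and the following variables collected for analysis". The list includes yes/no items for transfusion, for "More than one postoperative hemoglobin obtained", and for discharge delayed by the CBC result. It also has yes/no items for objective and subjective signs of anemia, length of stay, and 30-day readmission and emergency visits.

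Statistical Analysis begins its non-demographic part with "The percentage of subjects with hemoglobin less than 10 g/dL at POD1 will be evaluated" and goes on to signs of anemia, correlations, a t-test and two regression models. It names no main outcome.

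On what may follow an abnormal result, Background says: "Further evaluations of abnormal lab results may be additional blood work or more invasive procedures such as imaging tests or reoperation".

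**The concern.** A reader who carried out Statistical Analysis exactly as written would learn how far hemoglobin fell, how many patients were below 10 g/dL, how many had signs, and what predicts these. That reader would not learn in how many patients the CBC was followed by any action. A low hemoglobin is not itself a change in care; the Introduction says the whole clinical picture must be weighed before transfusing. The transfusion hypothesis has no planned estimate.

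At stake is the basis for the decision the protocol has in view, which is to stop routine testing in patients without signs. If the action rate is left to unplanned tabulation, the denominator, the components and the asymptomatic subset can all be chosen after the data are seen.

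A secondary concern is whether the listed data can support the missing outcome. The list has no imaging or reoperation item. Signs, transfusion and repeat hemoglobin carry no timing relative to the POD1 CBC.

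**Working it through.** **1. Planned analyses set against the question.** Apart from the description of demographics, Statistical Analysis contains six analyses:

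| Planned analysis | Outcome | Change in care? |
|---|---|---|
| Percentage | POD1 hemoglobin below 10 g/dL | No |
| Percentage | Signs of anemia | No |
| Pearson correlation | Postoperative hemoglobin | No |
| t-test, symptomatic vs asymptomatic | Hemoglobin change | No |
| Multiple linear regression | Hemoglobin decrease | No |
| Multiple logistic regression | Signs of anemia | No |

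The count is 0 of 6. The three care items collected (transfusion, repeat hemoglobin, CBC-related discharge delay) are assigned no analysis.

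**2. Listed data set against the actions the protocol names.** Background names further blood work, imaging and reoperation. The list covers further blood work through the repeat-hemoglobin item, but has no item for imaging or reoperation. Signs, transfusion and repeat hemoglobin are yes/no without date or time. The 30-day windows and the length of stay in days do not give the order relative to the POD1 CBC.

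**3. The plan's own figure.** Sample Size gives about 800 patients, from five years of caseload (800 / 5 = 160 a year) and comparison with studies of 629-1105. No event rate, precision target or power is stated, so 800 can be checked only for consistency. It lies within that range.

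**4. Precision of the missing outcome.** Inputs: 800 patients (Sample Size); 87-99.6% tested (Background, other cohorts); 50-90% of those tested without signs (my assumption, since the documents give no such figure).

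- Tested: 800 × 0.87 = 696; 800 × 0.996 = 797.
- Without signs: from 696 × 0.5 = 348 to 797 × 0.9 = 717.
- With 0 events, the exact (Clopper-Pearson) two-sided 95% upper limit is 1 − 0.025^(1/n): 1.05% at n = 348 and 0.51% at n = 717.
- With 3 events (an illustration): 3/348 = 0.86% (0.18-2.50%); 3/717 = 0.42% (0.09-1.22%).

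**5. The other end of the range.** Background reports that up to one third of tested patients in other cohorts needed some intervention based on the result. That figure is not limited to asymptomatic patients.

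- 696 / 3 = 232; 797 / 3 = 266.
- Three misclassified patients would move the proportion by 3/696 = 0.43 to 3/797 = 0.38 percentage points, which is negligible beside 33%.

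**6. Transfusion rate in all 800.** Exact 95% limits for illustrative counts: 0 events, upper limit 0.46%; 8 events (1%), 0.43-1.96%; 16 events (2%), 1.15-3.23%. The planned sample therefore supports a usefully narrow estimate, if one is planned.

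**The case against.** The care items are expressly gathered for analysis, and a yes/no percentage needs no special method, so the authors may well intend to tabulate them. The discharge-delay item already attributes the delay to the CBC. On this view the section is incomplete rather than the study defective. That stands in part: most of the repair uses data already planned, and it would go too far to say the study cannot answer its question. But an intention to tabulate does not fix the outcome, the denominator or the asymptomatic subset.

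A second objection is that the data gaps may not exist. Data Collection refers to an attached data collection sheet that is not in the text available for review, and field-level detail such as timing is what such a sheet would carry. This stands, so the point about imaging, reoperation and timing can only be conditional.

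Third, a patient with unrecorded imaging or reoperation would drop out of an any-change outcome only if she also had no repeat hemoglobin, transfusion or CBC-related delay. Some reoperations would also show in length of stay, readmission or emergency visits. This stands, and it limits any bias from those two fields.

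Fourth, a repeat hemoglobin may not be clinically relevant, which is the wording of the purpose. That is a fair matter of judgement, and it is met by reporting each component separately.

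**Conclusion.** The core point holds on the text alone. The stated question is about changes in care and the stated hypothesis is about transfusion, yet none of the six non-demographic analyses estimates either. The plan as written does not say how often the CBC changed care, in asymptomatic patients or overall. This should be corrected, and it does not depend on the unseen sheet.

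The missing imaging, reoperation and timing fields are a secondary point, valid only if the sheet also lacks them.

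A reader might infer that a few misclassified patients would reverse the conclusion, or that the gaps favour the minimal-utility hypothesis. The documents support neither. They set no threshold for minimal utility, so moving from 0 to 3 events cannot be shown to change a conclusion. At the one-third figure a few patients hardly matter. The direction is also not fixed. Unrecorded actions, or signs that began after the CBC, would lower the count in asymptomatic patients. A transfusion or an extra hemoglobin that preceded the POD1 result would raise it.

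The size of any bias is unknown. The 0.51-1.05% upper limits rest on the assumed 50-90% without signs, on testing rates from other cohorts, and on zero events, which is an illustration and not a forecast.

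**What to change.** **In Statistical Analysis (main change).** Name as main outcome the proportion with any change in care among patients who had a POD1 CBC and no signs of anemia, that is, neither the objective nor the subjective item recorded. Define change in care as postoperative transfusion, CBC-related discharge delay or repeat hemoglobin. Give an exact 95% CI and list each component separately, so that repeat hemoglobin can be read apart from the others. Report the same for all patients with a POD1 CBC. Report the transfusion rate with an exact 95% CI to match the hypothesis. The cost is a few proportions from data already planned.

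**In Data Collection (only if the attached sheet lacks them).** Add yes/no fields for imaging and for reoperation for suspected bleeding, and count both in the outcome. Add a before/after-CBC marker wherever a sign, transfusion or repeat hemoglobin is recorded. If timing is not collected, state that the signs-free group and the actions are classified without regard to order.

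The cost of the second part is not trivial. It is two fields in every chart, plus the marker in every chart with a sign or event. If 10-50% of patients have signs (assumed), that is 800 × 0.10 = 80 to 800 × 0.50 = 400 charts, within a 4-week abstraction running at 800 / 4 = 200 charts a week. It is best settled before abstraction starts, since later additions mean reopening charts.

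### Does the switch between ≤ 10 and < 10 g/dL for postoperative hemoglobin put a reported result at risk?

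*Combined protocol and SAP*

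**What the plan says.** The Data Collection section introduces its list with "Each chart will be reviewed and the following variables collected for analysis". Four items on that list matter here:

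- whether a blood count was drawn on the first postoperative morning: "CBC collected the morning of POD1";
- the value itself: "POD1 hemoglobin";
- a dichotomy of a hemoglobin value: "Postoperative hemoglobin ≤ 10 – yes/no";
- whether further values exist: "More than one postoperative hemoglobin obtained – yes/no".

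The Statistical Analysis section then names the summary to be reported: "The percentage of subjects with hemoglobin less than 10 g/dL at POD1 will be evaluated". It does not mention the yes/no item. The Sample Size section adds "Our anticipated sample size will be approximately 800 patients", a number based on expected surgical volume and the size of similar reviews, with no power calculation behind it.

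**The concern.** The two sections put the boundary on opposite sides of 10.0. The collected item includes a value of exactly 10.0, and the reported percentage excludes it. The item also lacks a unit and a day. Because some patients may have several postoperative values, it could in principle be set by a later one.

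The yes/no item is the only listed variable built on the 10 cut-off, so an analyst might simply count it. The published percentage would then not be the one the analysis section defines. The study asks whether a routine POD1 blood count is useful, so how often that test comes back low is a figure readers will look at. Hemoglobin is often recorded to one decimal place, in which case values of exactly 10.0 are not rare.

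**Working it through.** **The two definitions side by side**

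| Feature | Yes/no item (Data Collection) | Reported percentage (Statistical Analysis) |
|---|---|---|
| Inequality | ≤ 10 | < 10 |
| Unit | not stated | g/dL |
| Day | postoperative, no day given | POD1 |
| A POD1 value of 10.0 | counted | not counted |

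**Can the reported percentage be computed as defined?** Yes. It needs the POD1 value and a strict comparison with 10 g/dL. The POD1 value is a listed variable, and the field recording whether a POD1 count was drawn identifies who has one. The yes/no item is not needed, so its missing unit and day do not carry over to the percentage.

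**What else uses the cut-off?** Going through the Statistical Analysis section:

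- the Pearson correlation uses the hemoglobin level;
- the t-test uses change in hemoglobin, in symptomatic against asymptomatic patients;
- the linear regression uses the decrease in hemoglobin;
- the logistic regression uses the presence of signs of anemia.

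None of these splits hemoglobin at 10, and neither does the sample size.

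**How far would the percentage move if the yes/no item were counted instead?** The plan has no figure to reproduce and gives no hemoglobin mean, SD or recording precision, so this is an illustration under assumptions: POD1 hemoglobin normal with mean m and SD s, recorded to 0.1 g/dL, and all 800 patients with a value.

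- Share below 10: Φ((9.95 − m)/s)
- Share at or below 10: Φ((10.05 − m)/s)
- Shift: the difference between the two, times 800 for patients

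For m = 11.0 and s = 1.2: Φ(−0.875) = 19.1% and Φ(−0.792) = 21.4%. The shift before rounding is 2.35 points, and 0.0235 × 800 ≈ 19 patients.

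| Assumed mean, SD (g/dL) | < 10 | ≤ 10 | Shift (points) | Patients of 800 |
|---|---|---|---|---|
| 10.0, 1.0 | 48.0% | 52.0% | 4.0 | 32 |
| 10.5, 1.0 | 29.1% | 32.6% | 3.5 | 28 |
| 11.0, 1.2 | 19.1% | 21.4% | 2.3 | 19 |
| 11.5, 1.2 | 9.8% | 11.3% | 1.5 | 12 |
| 12.0, 1.0 | 2.0% | 2.6% | 0.5 | 4 |

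Over means of 10.0 to 12.0 and SDs of 1.0 to 1.5 the shift runs from about 0.5 to 4.0 points. The calculation covers the boundary alone. The effect of a later value setting the item cannot be sized from the documents.

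**The case for a change.** The strongest case for acting is that the shift, if it occurred, would always go one way and would be entirely avoidable. It is also not negligible in relative terms: at an assumed mean of 12.0 and SD of 1.0, the ≤ 10 percentage is about 1.27 times the < 10 percentage. Nor can it be dismissed as smaller than sampling error. At mean 10.5 and SD 1.0 the shift of 3.52 points exceeds the 95% half-width, 1.96 × √(0.291 × 0.709 / 800) = 3.15 points. The plan does not say in so many words which field supplies the percentage, and agreeing the two lines would cost almost nothing.

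The textual point stands: the two lines disagree. The consequence does not follow, because it needs an analyst to pass over a fully worded definition and the raw variable that serves it, and to count a differently worded item that the analysis section never mentions. The ambiguity about the day is also thin. The yes/no item comes after the POD1 value and before the question about repeat values, so POD1 is its natural reading. The attached data collection sheet is not in the text available here and may settle the item's operator, unit and day.

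**Conclusion.** The inconsistency is real but clerical, and no change to the plan follows. The reported percentage is completely defined where it is reported, and the variable needed to compute it is collected. An analyst working from the Statistical Analysis section arrives at the right number whatever the yes/no item says.

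The possible effect is confined to one descriptive percentage. It arises only if the item is tabulated in place of the raw value, and would then be about 0.5 to 4.0 points (roughly 4 to 32 of 800 patients). That range rests wholly on the assumed normal shape, the assumed means and SDs, recording to 0.1 g/dL and complete POD1 values. The stated purpose is whether routine testing changes care. Transfusion and delayed discharge, both collected, bear on that more directly than which side of the line a value of 10.0 falls.
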